9.2 Data analysis

For metabolomics analysis, peak extraction and grouping as well as retention time correction and alignment will be performed on XCMS Online.⁸³ Then, multivariate statistical analysis as

well as univariate will be done. First of all, regarding multivariate approaches, a principal component analysis will be applied to verify the analytical variability. Partial least squares-discriminant analysis (PLS-DA), the supervised version of PCA, will also be used to maximise the separation between different groups (i.e. control session versus inhibition session versus induction session). Then, the variable importance in projection (VIP) score calculated from the PLS-DA model may be applied to identify potential biomarkers.

In univariate analysis, a volcano plot will be performed to detect any significant changes in signal intensities before and after inhibition or induction as well as between PMs and NMs-RMs-UMs. The raw p-values will be adjusted by false discovery rate method to correct for multiple testing in the first case.

All the metabolomics analysis will be performed on the online platform Metaboanalyst.⁸⁴

The possible correlation between the blood MR OH-OPZ/OPZ and significant ions identified will be evaluated using Spearman's rank correlation. Values of $p < 0.05$ will be considered significant.

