Critères d'évaluation	
Critère d'évaluation principal :
 
Changement des intensités des ions déterminées par spectrométrie de masse selon le génotype (PMs versus NM_s-RM_s-UM_s) et selon les sessions. Les ions montrant un changement de facteur $\geq 1,5$ ou $\leq 0,67$ seront qualifiées de

	
biomarqueurs endogènes du CYP2C19. Les signaux chromatographiques seront détectés dans l'urine, plasma et vésicules extracellulaires dérivées du foie de volontaires sains par chromatographie liquide couplée à la spectrométrie de masse à haute résolution (LC-HRMS) à chaque session pour chacun des volontaires.
 
Critères d'évaluation secondaires :
 
Corrélation du phénotype avec les métabolites statistiquement significatifs mesurés en métabolomique.
 
Modèle de régression linéaire multiple pour prédire le phénotype du CYP2C19.

Evaluation de la tolérance	Les SAEs avec issue fatale et les SUSARs seront systématiquement relevés et rapportés dans les délais appropriés à la CCER et aux autorités.
Méthode statistique	
Critères primaires :
 
Analyses univariées : Volcano plot
 
Analyses multivariées : Analyse en composantes principales, régression des moindres carrés partiels
 
Critères secondaires :
 
Test de corrélation de Spearman

STUDY FLOWCHART

*The first tablet of fluvoxamine can be administrated during lunch on day 1 of session 1

STUDY DESIGN

Abbreviations

ADR	adverse drug reaction
AE	adverse event
ALAT	alanine-aminotransferase
ASAT	aspartate-aminotransferase
ASR	annual safety report
AUC	area under the concentration curve
CCER	commission cantonale d'éthique et de la recherche
eCRF	electronic case report form
CYP	cytochrome P450
DBS	dried blood spot
DDI	drug-drug interaction
EV	extracellular vesicle
FDA	US Food and Drug Administration
GGT	Gamma glutamyl transpeptidase
HUG	Geneva University Hospitals
IM	intermediate metabolizer
MR	metabolic ratio
NM	normal metabolizer
NMR	nuclear magnetic resonance
OClin	swiss ordinance on clinical trials on research involving humans
OH-OPZ	hydroxyomeprazole
OPZ	omeprazole
PM	poor metabolizer
RM	rapid metabolizer
SAE	serious adverse event
SUSAR	suspected unexpected serious adverse reaction
UM	ultra-rapid metabolizer
UMR	urinary metabolic ratio

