3. STUDY DESIGN

3.1 Overall description

The study will be an open-label study with a total of 40 healthy volunteers fulfilling inclusion/non-inclusion criteria, divided into 2 study groups: 10 healthy volunteers PMs and 30 NMs-RMs-UMs for CYP2C19 and participating in the three sessions:

- Session 1: urine and venous blood sampling. Determination of blood $MR_{OH-OPZ/OPZ}$ at baseline (no inhibitor administrated).
- Session 2: urine and venous blood sampling. Determination of blood $MR_{OH-OPZ/OPZ}$ after pre-treatment by fluvoxamine (strong inhibitor of CYP2C19).

- Session 3: urine and venous blood sampling. Determination of blood MR_{OH-OPZ/OPZ} after pre-treatment by rifampicin (strong inducer of CYP2C19).

Information:

At this step, the volunteer will have an interview with one of the co-investigators at the Clinical Pharmacology and Toxicology department and the study will be explained in detail. A sufficient time will be allowed before the inclusion session to guarantee sufficient time for reflection.

Inclusion:

Volunteers willing to participate and having signed the informed consent form (ICF) will undergo a clinical evaluation with a physician including liver and kidney tests, body mass index, genotyping (except if CYP2C19 genotype is already known) and a pregnancy test (women only). Women will be asked to use at least one physical contraceptive barrier (i.e. male or female condom, diaphragm, spermicide) throughout their study participation and 1 month after the end of the study, in addition of their hormonal contraception if applicable. In case of heavy menstrual bleeding, women will have to be recruited before or after their menstrual period to avoid the presence of blood in urine. In addition, all volunteers will be asked to avoid alcohol consumption on days of taking study drugs and 48 hours before day 0 of session 1. A volunteer code for the study will be assigned to each volunteer included in the study.

Only volunteers fulfilling the inclusion/non-inclusion criteria will be allocated to a study group.

Sessions course:

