Concerning the third session, participants will also be instructed to take two 300 mg tablets of rifampicin (Rimactan®) every evening for 10 days (10 doses in total) before the fourth visit. This regimen will begin at least 6 days after the third visit (session 2) and the last rifampicin intake will be done at the evening preceding the fourth visit (session 3).

Volunteers will be asked to back empty blisters of the drugs that they took home in order to verify compliance.

The total study duration will not exceed 32 days. Therefore, the first dose of fluvoxamine and rifampicin must be taken, at the latest, 9 days and 21 days after day 1 of session 1, respectively (see study design page 13).

The order of sessions is purposely not randomized due to unnecessity. Indeed, as it is solely a PK study performed on paired samples, there are no possible biases requiring randomization.

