3.2 Primary and secondary endpoints

Primary endpoint:

Fold-change in the intensities of features determined by mass spectrometry according to genotype (PMs versus NMs-RMs-UMs) and according to sessions. Metabolic features showing a fold-change ≥ 1.5 or ≤ 0.67 ³⁷ will be qualified as CYP2C19 endogenous biomarkers. Chromatographic signals will be detected in healthy volunteers' urine, plasma and liver-derived

extracellular vesicles by liquid chromatography coupled to high resolution mass spectrometry (LC-HRMS) at each session for each volunteer.

Secondary endpoint:

- Correlation of significant ions measured in metabolomics with OH-OPZ/OPZ blood ratio.
- Establishment of a multivariate linear regression model to predict CYP2C19 phenotype.

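### Section 9.2 fits ordinary PLS-DA to the three sessions as separate groups although the samples are paired; under some scaling and variance conditions VIP can then under-rank true markers

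*Protocol*

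**What the plan says.** Protocol section 9.2 (Data analysis) states that PLS-DA "will also be used to maximise the separation between different groups (i.e. control session versus inhibition session versus induction session". No volunteer term, within-volunteer step or scaling is named. The VIP "score calculated from the PLS-DA model may be applied to identify potential biomarkers", without a cut-off. A volcano plot, run alongside, is meant to "detect any significant changes in signal intensities before and after inhibition or induction". The synopsis lists the multivariate methods under the primary criteria: "Analyse en composantes principales, régression des moindres carrés partiels".

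The design is paired. Section 3.1 has 10 PMs and 30 NMs-RMs-UMs "participating in the three sessions", and justifies the fixed session order because "it is solely a PK study performed on paired samples". Section 9.1 sizes part 1 on a two-sided paired t-test.

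The qualifying rule is separate from PLS-DA: under section 3.2, features with a fold-change of at least 1.5 or at most 0.67 "will be qualified as CYP2C19 endogenous biomarkers".

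**The concern.** The three sessions are three states of the same people, not three groups of people. A model that sees only session labels leaves stable differences between volunteers in the data. If each ion is then divided by its total standard deviation, an ion that varies strongly between people but moves consistently within each person receives a small weight. Such an ion could fall down the VIP list behind ions that merely fluctuate by chance. What is at stake is the order in which candidates from part 1 are considered, and whether the multivariate analysis uses the pairing on which the sample size rests.

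**Working it through.** **Step 1: the protocol's own figure.** Inputs from section 9.1: 5000 features, so alpha = 0.05/5000 = 0.00001; power 80%; effect size dz = 1.156; two-sided paired t-test. Power is the probability that a noncentral t with n − 1 degrees of freedom and noncentrality dz × √n exceeds the critical value (the opposite tail is negligible). At n = 30 the noncentrality is 1.156 × √30 = 6.33 and the power 0.804; at n = 29 the power is 0.768. The stated 30 is reproduced, and it depends on pairing.

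**Step 2: when the volunteer matters to PLS-DA.** Write each intensity as volunteer mean plus within-volunteer deviation. In a complete three-session design the centred session labels sum to zero within each volunteer, so the volunteer means drop out of the cross-product X'Y. A numerical check agrees (largest difference about 1e-14). Without scaling, the first-component weights are therefore the same with and without within-volunteer centring.

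Scaling by total SD changes this. Let ICC be the between-volunteer share of an ion's variance. Ignoring the ion's own session effect, total SD = within SD / √(1 − ICC), so the weight is multiplied by √(1 − ICC):

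- ICC 0.1: √0.9 = 0.95
- ICC 0.5: √0.5 = 0.71
- ICC 0.8: √0.2 = 0.45
- ICC 0.9: √0.1 = 0.32

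A marker with ICC 0.9 thus competes with ions of ICC 0.1 at 0.32/0.95, about one third of the weight. If all ions share one ICC, the factor is common and cancels.

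**Step 3: simulation.** 30 volunteers, 3 sessions, 5000 ions, 20 true markers with dz 1.156 (a shift of 1.156 × √2 = 1.63 within-volunteer SDs), two components, 8 replicates per setting. Assumed, because the documents give no value: autoscaling, and the ICCs shown. Entries are the share of the 20 true markers in the top 20 by VIP, ordinary versus within-volunteer PLS-DA.

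| Marker ICC | One drug, all ions same ICC | One drug, other ions mixed 0.1–0.9 | Opposite response to both drugs, other ions mixed |
|---|---|---|---|
| 0.2 | 0.98 vs 0.99 | 0.98 vs 0.98 | 1.00 vs 1.00 |
| 0.5 | 0.98 vs 0.99 | 0.96 vs 0.99 | 1.00 vs 1.00 |
| 0.8 | 0.94 vs 0.98 | 0.60 vs 1.00 | 0.99 vs 1.00 |
| 0.9 | 0.98 vs 1.00 | 0.17 vs 0.99 | 0.81 vs 1.00 |

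Repeats of the one-drug, mixed-ICC case:

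- 15 replicates: 0.67 vs 0.99 (ICC 0.8) and 0.20 vs 0.99 (ICC 0.9); at ICC 0.7, 0.87 vs 1.00.
- A run with 2000 ions: about 0.7 and 0.3, vs 0.98–0.99. For opposite responses this run gave about 0.92–0.99 vs 1.00.

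In the worst cell of the table (0.17) the median rank of the true markers was about 98 of 5000, against 10.5 with within-volunteer centring. Across the settings run, 0.99–1.00 of true markers still had VIP above 1 (an assumed cut-off).

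**The case against.** The strongest reply is that the loss rests on conditions the protocol does not state.

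- **Scaling.** It is a pre-processing choice and not part of PLS-DA. A reader might infer that ordinary PLS-DA always divides by total variance; neither the method nor the protocol says so. Unscaled, at marker ICC 0.9, recall was 0.99 vs 0.99 for one drug and 1.00 vs 1.00 for both. This stands, with one limit: that run gave all ions the same within-volunteer variance. When ions had the same total variance instead, unscaled recall fell to 0.72 (ICC 0.8) and 0.16 (ICC 0.9), so leaving out scaling is no dependable remedy.
- **ICC.** No section gives one. A reader might expect a high ICC because the enzyme is polymorphic, but part 1 is sized on NMs-RMs-UMs, IMs are excluded, and section 4.4 pools the three types because it expects small differences between them. This stands: a high marker ICC is possible but not shown.
- **Response pattern.** Sections 5.1.2 and 5.1.3 expect metabolites to fall under fluvoxamine and rise under rifampicin, which is the case with the smaller loss. This stands.
- **Role of VIP.** It is optional, has no cut-off, and runs beside a volcano plot. The top-20 list is a yardstick chosen for this check, not a rule of the protocol. This stands.
- **The analysis plan.** It is not at hand and may specify a multilevel model. Naming PLS-DA does not rule that out, but the protocol's description of sessions as different groups points the other way and should be corrected where it stands.

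**Conclusion.** The mismatch is real: section 9.2 describes an analysis of separate groups for data that the protocol elsewhere treats as paired. In the settings run, the within-volunteer version ranked as well as or better than the ordinary one, up to simulation noise. With autoscaled ions, mixed ICC and response to one drug, top-20 recall was about 0.7 (0.60 in one run) against about 0.99 at marker ICC 0.8, and about 0.2 to 0.3 against 0.99 at ICC 0.9. It was generally small for opposite responses (most visible at ICC 0.9) and negligible with a similar ICC in all ions.

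Two stronger conclusions might be drawn and are not supported. The first is that true markers are masked outright: the loss needs both the scaling and the ICC contrast, and even then markers mostly drop in rank and do not disappear. The second is that half of the primary analysis is wasted, because the synopsis lists partial least squares under the primary criteria. The synopsis gives it no decision role, and qualification is by fold-change. The effect is on the multivariate ranking of candidates, not on the primary qualifying rule. The change is worth making because it is cheap and brings the analysis into line with the design.

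**What to change.** In section 9.2, for the session contrasts only, replace ordinary PLS-DA by multilevel PLS-DA: for each ion subtract the volunteer's mean over the three sessions, then autoscale, then fit. Keep all samples of a volunteer together in cross-validation, and permute session labels within volunteer. The comparison of PMs with NMs-RMs-UMs at baseline is between people and must not be centred in this way.

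Also state how volunteers with fewer than three sessions enter. Section 9.3 replaces withdrawals, but section 5.5 keeps and analyses their data. A single session carries no information after centring, and two sessions break the balance used in step 2.

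The cost is a modest amount of extra analysis and a few sentences of text. Section 9.2 commits the metabolomics analysis to one online platform, and the documents do not show whether it supports volunteer-wise cross-validation and restricted permutation, so part of the work may have to be done elsewhere. No further volunteers, visits or samples are needed.

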Rationnel et Objectifs	
Le cytochrome P450 2C19 (CYP2C19) est l'enzyme responsable du métabolisme de médicaments fréquemment prescrits en clinique comme l'oméprazole, un antiacide inhibiteur de la pompe à proton (IPP), le citalopram, un antidépresseur inhibiteur sélectif de la recapture de la sérotonine (ISRS) ou le clopidogrel, un antiagrégant plaquettaire. Le CYP2C19 présente une importante variabilité interindividuelle de son activité dans la population générale due, notamment, à un fort polymorphisme génétique, avec une trentaine de variants alléliques identifiés à ce jour. Ceci résulte en cinq phénotypes distincts dans son activité : le phénotype métaboliseur lent (PM), le phénotype métaboliseur intermédiaire (IM), le phénotype métaboliseur normal (NM), le phénotype métaboliseur rapide (RM) et le phénotype métaboliseur ultra-rapide (UM).
 
Pour caractériser l'activité du CYP2C19, il existe différentes méthodes de phénotypage à savoir l'administration d'une substance-test métabolisée de manière spécifique par le CYP2C19 et la mesure de paramètres pharmacocinétiques, tels que l'aire sous la courbe (AUC), ou des ratios métaboliques entre les concentrations de la molécule-mère et de son métabolite. Les substances-tests les plus utilisées sont l'oméprazole (OPZ) et la méthénytoïne. Il est également possible de mesurer le phénotype de plusieurs isoformes des CYPs simultanément avec le phénotypage mixte, tel que le « Geneva cocktail » développé aux HUG. Ce dernier est composé de 6 substances-tests permettant de phénotyper simultanément 6 isoformes des CYPs, dont l'OPZ pour le CYP2C19.
 
Malgré une bonne tolérance de ce cocktail, certains patients peuvent être réticents à l'administration de médicaments de manière exogène et il n'est parfois pas possible de les administrer à certains patients (e.g. femmes enceintes, enfants, personnes âgées). Il convient par ailleurs d'attendre 2h après l'ingestion du « Geneva cocktail » avant d'effectuer la prise de sang, ce qui peut poser quelques contraintes pratiques en clinique.
 
L'utilisation de biomarqueurs endogènes de mesure de l'activité des CYPs permettrait ainsi de s'affranchir de ces obstacles et de rendre la pratique moins invasive et plus acceptable pour les patients. Une récente étude consacrée au CYP2D6 conduite au sein de notre service a permis d'identifier de nouveaux biomarqueurs endogènes pour cet isoforme, à savoir la solanidine, un alcaloïde aglycone très commun, et ses dérivés.
 
Le but de notre étude est d'identifier de nouveaux biomarqueurs endogènes pour mesurer (phénotyper) l'activité du CYP2C19 par métabolomique non ciblée.
 
Les volontaires sains seront stratifiés en deux groupes selon leur phénotype pour le CYP2C19 : les sujets PMs et NM-RMs-UMs. Les sujets IMs seront exclus afin d'observer des différences plus significatives au sein des deux groupes.
 
Objectif primaire :
 
 - Partie 1 : mise en évidence de potentiels substrats et/ou métabolites endogènes du CYP2C19 par métabolomique non ciblée sur des échantillons urinaires, plasmatiques et de vésicules extracellulaires dérivées du foie prélevés avant (baseline, session 1) et après administration répétée de fluvoxamine (inhibition enzymatique du CYP2C19, session 2) ainsi qu'après administration répétée de rifampicine (induction enzymatique du CYP2C19, session 3). - Partie 2 : identification des substrats et/ou métabolites endogènes du CYP2C19 parmi les composés mis en évidence dans la partie 1 par analyse semi-quantitative ciblée sur des échantillons urinaires, plasmatiques et de vésicules extracellulaires dérivées du foie des volontaires sains PMs et NM-RMs-UMs à la baseline (i.e sans administration préalable de fluvoxamine ou de rifampicine). 
Objectifs secondaires :
 
 - Identification des substrats et/ou des métabolites endogènes du CYP2C19 à l'aide de bases de données internes ou externes, par fragmentation en LC-MS/MS ou à l'aide de standards de référence. - Corrélation des concentrations plasmatiques et/ou urinaires et/ou de vésicules extracellulaires dérivées du foie d'un substrat et/ou un métabolite endogène du CYP2C19 avec le phénotype (ratio sanguin OH-oméprazole/oméprazole) et/ou le génotype du CYP2C19.

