Méthode	
Le projet consiste en trois parties expérimentales :
 
 - Partie 1 : mesure de l'impact d'un inhibiteur du CYP2C19, la fluvoxamine, sur le métabolome urinaire, plasmatique et de vésicules extracellulaires dérivées du foie - Partie 2 : mesure de l'impact d'un inducteur du CYP2C19, la rifampicine, sur le métabolome urinaire, plasmatique et de vésicules extracellulaires dérivées du foie - Partie 3 : mise en évidence des biomarqueurs du CYP2C19 par mesure de l'impact des polymorphismes du CYP2C19 sur les composés affectés dans les parties 1 et 2. 
Il s'agit d'une étude ouverte à design croisé chez des volontaires sains répartis en deux groupes selon leur génotype du CYP2C19 (PMs et NMs-RMs-UMs). Trois sessions auront lieu pour chaque sujet :
 
Session 1 : prélèvements plasmatique et urinaire ainsi que la détermination du ratio sanguin OH-oméprazole/oméprazole à la baseline par prise de sang capillaire.
 
Session 2 : idem session 1 avec prise au préalable de 50 mg de fluvoxamine pendant 7 jours consécutifs (inhibiteur fort du CYP2C19).
 
Session 3 : idem session 1 avec prise au préalable de 600 mg de rifampicine pendant 10 jours consécutifs (inducteur fort du CYP2C19).
 
A chaque session, une récolte urinaire sur 24h est effectuée, suivie d'une prise de sang veineux (6 x 6 ml) le matin à jeun. Le phénotypage a ensuite lieu avec la prise d'oméprazole à 10 mg, suivie d'une prise de sang capillaire (4 x 10 µl) après 2h. Après la session 1, la prise de fluvoxamine a lieu durant 7 jours consécutifs (administration au total de 7 doses de fluvoxamine à 50 mg), pouvant commencer au moment du repas de midi lors du déroulement de la session 1. La dernière prise de fluvoxamine doit avoir lieu 2h avant l'administration d'oméprazole à 10 mg lors de la troisième visite (jour 11±4j, session 2). Enfin, la prise de rifampicine aura lieu au moins 6 jours après la session 2, tous les soirs durant 10 jours consécutifs (administration au total de 10 doses de rifampicine à 600 mg). La dernière prise de rifampicine doit avoir lieu le soir de la veille de l'administration d'oméprazole à 10 mg lors de la quatrième visite (jour 27±4j, session 3).

Nombre de volontaires	40 volontaires sains : 10 PMs et 30 NMs-RMs-UMs
Durée de l'étude	Au minimum 24 jours et au maximum 32 jours par volontaire

[figure not shown]

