will be excluded. Moreover, to ensure the recruitment of psychically healthy subjects, risk of depression and/or suicidal ideation will be assessed with the Beck Depression Inventory (see Section 4.6). Antidepressant discontinuation syndrome (ADS) has been described in case of abrupt cessation generating the following symptoms: dizziness, sensorial troubles, sleep disorders, agitation, anxiety, nausea, tremor, sweating, headaches, and emotional instability. In most patients, the intensity of these symptoms was minor and disappeared spontaneously.⁴⁷ Moreover, ADS is unlikely when treatments are taken less than 5-8 weeks.^{60,61} In this study, a total of 7 doses of fluvoxamine 50 mg spread over 7 days will be given to volunteers, which minimizes the risk of experiencing adverse events and ADS. Fluvoxamine acts as a potent inhibitor of CYP2C19 and CYP1A2, and a moderate inhibitor of CYP2C9, CYP2D6 and CYP3A4.^{15,16,47,62,63} It is mainly metabolized to fluvoxamine acid through CYP2D6, representing its major metabolic pathway, along with minor contributions of CYP1A2.^{50,56-59,63} In this clinical trial, we will administer fluvoxamine for 7 days to be able to observe a decrease in the concentration of endogenous CYP2C19 metabolites with a relatively long half-life. It is not relevant to detect metabolites with a longer half-life as it may not allow the detection of rapid changes in the phenotype. Moreover, the steady-state of fluvoxamine should be almost reached after 7 days of dosing at 50 mg.^{48,49}

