9. STATISTICS

9.1 Number of subjects

The data from Bosilkovska et al.²⁴, Magliocco et al.³⁷, Zhou et al.¹¹ and Akasaka et al.⁴⁰ were used as a basis to measure the effect size required for our clinical study and the number of subjects required for each study group.

The software G*Power (version 3.1.9.7) was used to calculate the sample size for a two-sided paired samples t-test with a power ($1-\beta$) of 80% for the part 1 of the study. The Bonferroni correction was applied to adjust the p-value (α = type 1 error) in order to correct for multiple tests as it is the case in metabolomics analyses. Therefore, p-value is divided by the number of expected features, which was defined as 5000 according to the number of metabolic features obtained after data processing in the Magliocco et al. clinical study, of which metabolomics were used to prospect on CYP2D6 endogenous biomarkers³⁷. Consequently, the p-value used for the power calculation will then be $1 \cdot 10^{-5}$. Moreover, the effect size obtained for the statistical analysis and based on the Bosilkovska et al. trial is 1.156. After entering all these parameters, a sample size of 30 is measured, which implies that 30 healthy volunteers NMs-RMs-UMs are required to observe a difference between control session, inhibition session and induction session in the part 1 of the study.

For the second part of the study (validation of identified features in the first part), a semi-quantitative targeted analysis will be performed. In Zhou et al.¹¹ study, 14% of the total number of participants were PM individuals among all the study participants and were enrolled to confirm a statistical difference between CYP2C19 PMs and non-PMs in the pharmacokinetic of a single 20 mg dose of omeprazole. Moreover, 35% of the total number of patients were PMs in the study of Akasaka et al.⁴⁰ where PMs and non-PMs were compared to have a significant difference between serum EETs levels (potential endogenous biomarker of CYP2C19).

Following these data, 10 PM individuals i.e. 10 subjects, which is 25% of the total number of our subjects (mean proportion of Zhou et al. and Akasaka et al. studies when combined), will be recruited. Therefore, already genotyped healthy volunteers known from our database or new ones will be contacted and if achievable, 10 PMs and 30 NMs-RMs-UMs (40 in total) subjects will be recruited and compared to each other at baseline.

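### The genotype comparison that confirms candidate biomarkers is left without multiplicity adjustment, and the biomarker label is given on fold-change alone

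*Protocol*

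**What the plan says.** Section 9.2 describes one volcano-plot analysis with two comparisons, "to detect any significant changes in signal intensities before and after inhibition or induction as well as between PMs and NMs-RMs-UMs". The next sentence limits the adjustment: "The raw p-values will be adjusted by false discovery rate method to correct for multiple testing in the first case". No other section adjusts the genotype comparison. The Bonferroni level in section 9.1 serves only the part 1 sample size.

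The genotype comparison is not incidental:

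- Section 3.2 puts it in the primary endpoint: "Fold-change in the intensities of features determined by mass spectrometry according to genotype (PMs versus NMs-RMs-UMs) and according to sessions".
- Section 9.1 makes it the confirmatory step: "For the second part of the study (validation of identified features in the first part), a semi-quantitative targeted analysis will be performed".
- The synopsis objectives describe part 2 as "identification des substrats et/ou métabolites endogènes du CYP2C19 parmi les composés mis en évidence dans la partie 1 par analyse semi-quantitative ciblée". The synopsis methods, which number the parts differently, describe the same step as "par mesure de l'impact des polymorphismes du CYP2C19 sur les composés affectés dans les parties 1 et 2".

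The rule for calling an ion a biomarker is in section 3.2 and is repeated in the synopsis endpoints. It covers "Metabolic features showing a fold-change ≥ 1.5 or ≤ 0.67" and contains no p-value, adjusted or raw.

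**The concern.** The genotype comparison separates compounds that depend on CYP2C19 from those that merely respond to the drugs. Section 5.1.2 says "Fluvoxamine acts as a potent inhibitor of CYP2C19 and CYP1A2, and a moderate inhibitor of CYP2C9, CYP2D6 and CYP3A4", and section 5.1.3 says that rifampicin strongly induces CYP2C8, 2C9 and 3A4/5 as well as 2C19, and weakly induces 1A2 and 2B6. A compound can therefore be a true finding in part 1, correctly passing FDR there, and still have no relation to CYP2C19 genotype. Controlling error in part 1 says nothing about how many such compounds pass the genotype step by chance.

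Because the restriction is written into the protocol, a SAP that follows it would leave this comparison unadjusted. At stake is how far the label in section 3.2 can be trusted.

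**Working it through.** **The plan's own figure.** Section 9.1 gives a two-sided paired t-test, 80% power, 5000 expected features and effect size 1.156. Then α = 0.05/5000 = 1×10⁻⁵, and the noncentrality is 1.156×√n with n−1 df. Power is 76.8% at n = 29 and 80.4% at n = 30, so the stated 30 reproduces. Part 1 was sized with strict multiplicity control. No error rate is stated for the genotype comparison.

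**What the part 1 filter does.** If 100 ions are selected at FDR 5%, about 0.05×100 = 5 are chance findings, and 0.05×5 = 0.25 would also pass p<0.05 for genotype. The two steps together deal well with part 1 chance findings. They do not deal with true drug responders that are null for genotype. For k independent ions of that kind tested at 0.05, the expected number of false hits is 0.05k and the chance of at least one is 1−0.95^k:

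- k = 10: 0.5 expected, 40%
- k = 100: 5 expected, 99%

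These figures ignore the fold-change rule, so they are upper values.

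**The fold-change rule as a filter.** With 10 versus 30, the standard error of the log difference is s×√(1/10+1/30) = 0.365s, where s is the between-subject SD of natural-log intensity. A null ion is labelled when its log difference exceeds ln 1.5 = 0.405 or falls below ln 0.67 = −0.400.

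- s = 0.3: SE 0.110, z about 3.7; about 0.02% of null ions pass
- s = 0.5: SE 0.183, z = 2.22 and 2.19; 1.3% + 1.4% = 2.7%
- s = 0.8: SE 0.292, z = 1.39 and 1.37; 8.3% + 8.5% = 16.8%

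The smallest difference with p<0.05 is 2.024×0.365 = 0.74 SD. This equals a 1.5-fold change at s = 0.405/0.74 = 0.55. Above that, the p-value is usually the stricter filter.

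**False share among hits.** I simulated 10 versus 30 with a pooled t-test on log intensities (38 df), independent features and Benjamini-Hochberg at 5%. The fold-change rule was required in both p-value rows. The true difference is 1.5 SD.

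| Candidates | Rule | s = 0.3 | s = 0.5 | s = 0.8 |
|---|---|---|---|---|
| 1 true of 10 | p<0.05 | 0.1% | 11% | 20% |
| 1 true of 10 | FDR-adjusted | 0.1% | 4% | 4% |
| 5 true of 100 | p<0.05 | 0.5% | 31% | 47% |
| 5 true of 100 | FDR-adjusted | 0.5% | 5% | 5% |
| 5 true of 100 | fold-change only (section 3.2 as written) | under 1% | 32% | 75% |

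The last row shows that editing section 9.2 alone would not change who gets the label.

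**Power with the fold-change rule, unadjusted then adjusted.**

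- 1.5 SD, s = 0.5: 97% to 87% (10 candidates), 97% to 78% (100)
- 1.5 SD, s = 0.3: 66% to 65% (100)
- 1.0 SD, s = 0.5: 69% to 23% (100)

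**The case against.** The best defence is that the design is deliberate: correct the large screen, then test a short targeted list without correction, with correlation to the omeprazole ratio and in vitro work (section 2.9) to follow. In discovery work a false lead costs an assay, while a missed marker defeats the aim, and there are only 10 PMs. The power loss is real and can be large. However, adjusting a short validation list is ordinary practice. Unadjusted hits can still go forward as leads, and section 3.2 does not make the later steps a condition of the label.

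Direction is a fair point too. Sections 5.1.2 and 5.1.3 expect CYP2C19 metabolites to fall under fluvoxamine and rise under rifampicin. Counting only genotype hits in the expected direction roughly halves the false hits: for 5 true of 100 at s = 0.5, the unadjusted false share drops from about 31% to 17%. The protocol does not make this a rule.

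It also stands that the label comes from section 3.2 and not from the adjustment sentence, so both must change.

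A reader might go further and infer that some 5000 features are tested unadjusted by genotype, giving about 0.05×5000 = 250 false hits. The documents do not support that as the plan. Section 9.1 and the synopsis confine the genotype step to a targeted analysis of compounds from part 1, so the 5000-feature case is only an off-design bound. Nor is the lack of a detailed definition of the test family a separate fault, since a SAP may hold it.

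**Conclusion.** The point holds and should be fixed. The genotype comparison, part of the primary endpoint and the validation step, is excluded from multiplicity adjustment by a written rule, and section 3.2 adds no significance condition of its own. The effect is negligible at a log-SD near 0.3 and material from about 0.5. There the unadjusted false share is about 11% (1 true of 10) to 31% (5 true of 100), against 4% to 5% when adjusted.

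These sizes rest on assumptions: number of candidates, share that are true, variability, effect size, independence, and a 0.05 genotype threshold. Section 9.2 states 0.05 only for the Spearman correlation. The figures show that the choice can matter. They do not show that most ions reported by this trial will be false.

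**What to change.** 1. In section 9.2, apply FDR adjustment to both the session and the genotype comparisons, and name the part 1 candidates tested as the family for the genotype comparison.
2. In section 3.2 and the matching synopsis endpoint, require FDR-adjusted significance in the genotype comparison, in addition to the fold-change threshold, before an ion is called a CYP2C19 endogenous biomarker.
3. Report raw p-values alongside. Treat ions that pass only unadjusted as exploratory leads for the planned in vitro work.

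No extra samples or visits are needed. The price is the power loss shown above, which is smaller when the candidate list is short. If the sponsor prefers no adjustment, the protocol should say so, give the reason, and not describe the resulting ions as validated.
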